7. SAMPLE SIZE JUSTIFICATION

Approximately 72 subjects will be enrolled so that approximately 60 healthy volunteers complete this study. This study is designed to test noninferiority (NI) of lasmiditan relative to placebo, with a diphenhydramine test versus placebo to confirm the sensitivity of the simulator to detect treatment effects. The following assumptions were made in the sample size computation: (a) standard deviation (SD) of differences between lasmiditan and placebo within subject for standard deviation of lateral position (SDLP) is approximately 9.5 cm; (b) the true difference between lasmiditan doses and placebo is 0; and (c) the NI margin is proposed to be 4.4 cm, which is the effect seen with 0.05% of blood alcohol count. Under these assumptions, a sample of 60 subjects would provide >90% power to establish NI of either dose of lasmiditan compared to placebo in terms of the primary end point, SDLP. This sample size is more than adequate to detect diphenhydramine differences, which are anticipated to exceed the NI margin, from placebo.

Subjects who are randomized but who do not complete all 4 periods during the Treatment Phase may be replaced. Replacement subjects will enter the same treatment sequence as the original subjects to complete all 4 periods.

8. DEFINITION OF ANALYSIS POPULATIONS

The “Safety” population will consist of all enrolled subjects, whether or not they completed all protocol requirements.

The “Pharmacokinetic” population will consist of all subjects who received at least one dose of the investigational products and have evaluable PK data. Subjects may be excluded from the PK summary statistics and statistical analysis if a subject has an adverse event (AE) of vomiting that occurs at or before 2 times median t_{max} .

The “Pharmacodynamic” population will consist of all subjects who received at least one dose of the investigational products and have evaluable PD data. Subjects may be excluded from the PD summary statistics and statistical analysis if a subject has an AE of vomiting that occurs at or before 2 times median t_{max} .

All protocol deviations that occur during the study will be considered for their severity/impact and will be taken into consideration when subjects are assigned to analysis populations.

9. STATISTICAL METHODOLOGY

9.1 General

Data listings will be provided for all data that are databased. For continuous data, summary statistics will include the arithmetic mean, arithmetic SD, median, min, max and N; for log-normal data (e.g. the PK parameters: area under the concentration versus time curve [AUCs] and the maximum observed drug concentration [C_{max}]) the geometric mean and geometric coefficient of variation (CV%) will also be presented. For categorical data, frequency count and percentages will be presented. Data listings will be provided for all subjects up to the point of withdrawal, with any subjects excluded from the relevant population highlighted. Summary

statistics and statistical analyses will generally only be performed for subjects included in the relevant analysis population. For the calculation of summary statistics and statistical analysis, unrounded data will be used.

Mean change from baseline is the mean of all individual subjects' change from baseline values. Each individual change from baseline will be calculated by subtracting the individual subject's baseline value from the value at the timepoint. The individual subject's change from baseline values will be used to calculate the mean change from baseline using a SAS procedure such as Proc Univariate.

Data analysis will be performed using SAS[®] Version 9.4 or greater.

9.2 Demographics and Subject Disposition

Subject disposition will be listed. The demographic variables age, sex, race, ethnicity, country of enrolment, site ID, body weight, height, and body mass index (BMI) will be summarized and listed.

9.3 Pharmacokinetic Assessment

9.3.1 Pharmacokinetic Analysis

Pharmacokinetic parameter estimates will be determined using non-compartmental procedures in validated software program (Phoenix WinNonlin Version 6.4 or later).

Concentrations for lasmiditan and metabolites based on predose samples evaluated for periods 2, 3, 4 may be used for characterizing PK for the preceding period as an additional timepoint (ie 72 hours)

Plasma concentrations of lasmiditan (LY573144) and its metabolites (M7, M8, (S,R)-M18, and (S,S)-M18) will be used to determine the following PK parameters, when possible:

Parameter	Units	Definition
C_{\max}	ng/mL	maximum observed drug concentration
t_{\max}	h	time of maximum observed drug concentration
AUC(0- ∞)	ng.h/mL	area under the concentration versus time curve from time zero to infinity
AUC(0- t_{last})	ng.h/mL	area under the concentration versus time curve from time zero to time t , where t is the last time point with a measurable concentration
%AUC(t_{last} - ∞)	%	percentage of AUC(0- ∞) extrapolated
$t_{1/2}$	h	half-life associated with the terminal rate constant (λ_z) in non-compartmental analysis
CL/F	L/h	apparent total body clearance of drug calculated after extra-vascular administration (LY573144 only)
V_z/F	L	apparent volume of distribution during the terminal phase after extra-vascular administration (LY573144 only)
V_{SS}/F	L	apparent volume of distribution at steady state after extra-vascular administration (LY573144 only)
MR		metabolic ratio ^a

a: no molar correction will be applied since the metabolites are very similar in molecular weight and within 5% of the molecular weight for lasmiditan.

Plasma concentrations of diphenhydramine will be listed and summarized.

Additional PK parameters may be calculated, as appropriate. The software and version used for the final analyses will be specified in the clinical study report. Any exceptions or special handling of data will be clearly documented within the final study report.

Formatting of tables, figures and abbreviations will follow the Eli Lilly Global PK/PD/TS Tool: NON-COMPARTMENTAL PHARMACOKINETIC STYLE GUIDE. The version of the tool effective at the time of PK analysis will be followed.

9.3.2 General Pharmacokinetic Parameter Rules

- Actual sampling times will be used in the final analyses of individual PK parameters, except for non-bolus pre-dose sampling times which will be set to zero.
- C_{\max} and t_{\max} will be reported from observed values. If C_{\max} occurs at more than one time point, t_{\max} will be assigned to the first occurrence of C_{\max} .
- AUC parameters will be calculated using a combination of the linear and logarithmic trapezoidal methods (linear-log trapezoidal rule). The linear trapezoidal method will be applied up to t_{\max} and then the logarithmic trapezoidal method will be used after t_{\max} . The minimum requirement for the calculation of AUC will be the inclusion of at least three consecutive plasma concentrations above the lower limit of quantification (LLOQ), with at least one of these concentrations following C_{\max} .

- AUC(0-∞) values where the percentage of the total area extrapolated is more than 20% will be flagged. Any AUC(0-∞) value excluded from summary statistics will be noted in the footnote of the summary table.
- Half-life ($t_{1/2}$) will be calculated, when appropriate, based on the apparent terminal log-linear portion of the concentration-time curve. The start of the terminal elimination phase for each subject will be defined by visual inspection and generally will be the first point at which there is no systematic deviation from the log-linear decline in plasma concentrations. Half-life will only be calculated when a reliable estimate for this parameter can be obtained comprising of at least 3 data points. If $t_{1/2}$ is estimated over a time window of less than 2 half-lives, the values will be flagged in the data listings. Any $t_{1/2}$ value excluded from summary statistics will be documented in the footnote of the summary table.
- A uniform weighting scheme will be used in the regression analysis of the terminal log-linear portion of the concentration-time curve.
- The parameters based on last predicted quantifiable drug concentration (C_{last}) will be reported.

9.3.3 Individual PK Parameter Rules

- Only quantifiable concentrations will be used to calculate PK parameters with the exception of special handling of certain concentrations reported below the lower limit of quantitation (BQL). Plasma concentrations reported as BQL will be set to a value of zero when all of the following conditions are met:
 - The compound is non-endogenous.
 - The samples are from the initial dose period for a subject or from a subsequent dose period following a suitable wash-out period.
 - The time points occur before the first quantifiable concentration.
- All other BQL concentrations that do not meet the above criteria will be set to missing.
- Also, where two or more consecutive concentrations are BQL towards the end of a profile, the profile will be deemed to have terminated and therefore any further quantifiable concentrations will be set to missing for the calculation of the PK parameters unless it is considered to be a true characteristic of the profile of the drug.

9.3.4 Individual Concentration vs. Time Profiles

- Individual concentrations will be plotted utilizing actual sampling times.
- The terminal point selections will be indicated on a semi-logarithmic plot.

9.3.5 Average Concentration vs. Time Profiles

- The average concentration profiles will be graphed using scheduled (nominal) sampling times.

- The average concentration profiles will be graphed using arithmetic average concentrations.
- The pre-dose average concentration for single-dose data from non-endogenous compounds will be set to zero.
- Concentrations at a sampling time exceeding the sampling time window specified in the protocol, or $\pm 10\%$, will be excluded from the average concentration profiles.
- Concentrations excluded from the mean calculation will be documented in the final study report.
- A concentration average will be plotted for a given sampling time only if 2/3 of the individual data at the time point have quantifiable measurements that are within the sampling time window specified in the protocol or $\pm 10\%$. An average concentration estimated with less than 2/3 but more than 3 data points may be displayed on the mean concentration plot if determined to be appropriate and will be documented within the final study report.

9.3.6 Treatment of Outliers during Pharmacokinetic Analysis

Application of this procedure to all PK analyses is not a requirement. Rather, this procedure provides justification for exclusion of data when scientifically appropriate. This procedure describes the methodology for identifying an individual value as an outlier for potential exclusion, but does not require that the value be excluded from analysis. The following methodology will not be used to exclude complete profiles from analysis.

Data within an Individual Profile

A value within an individual profile may be excluded from analysis if any of the following criteria are met:

- For PK profiles during single dosing of non-endogenous compounds, the concentration in a pre-dose sample is quantifiable.
- For any questionable datum that does not satisfy the above criteria, the profile will be evaluated and results reported with and without the suspected datum.

Data between Individual Profiles

1. If $n < 6$, then the dataset is too small to conduct a reliable range test. Data will be analyzed with and without the atypical value, and both sets of results will be reported.
2. If $n \geq 6$, then an objective outlier test will be used to compare the atypical value to other values included in that calculation:
 - a. Transform all values in the calculation to the logarithmic domain.
 - b. Find the most extreme value from the arithmetic mean of the log transformed values and exclude that value from the dataset.
 - c. Calculate the lower and upper bounds of the range defined by the arithmetic mean $\pm 3 \cdot SD$ of the remaining log-transformed values.

- d. If the extreme value is within the range of arithmetic mean $\pm 3 \times \text{SD}$, then it is not an outlier and will be retained in the dataset.
- e. If the extreme value is outside the range of arithmetic mean $\pm 3 \times \text{SD}$, then it is an outlier and will be excluded from analysis.

If the remaining dataset contains another atypical datum suspected to be an outlier and $n \geq 6$ following the exclusion, then repeat step 2 above. This evaluation may be repeated as many times as necessary, excluding only one suspected outlier in each iteration, until all data remaining in the dataset fall within the range of arithmetic mean $\pm 3 \times \text{SD}$ of the log-transformed values.

Reporting of Excluded Values

Individual values excluded as outliers will be documented in the final report. Approval of the final report will connote approval of the exclusion.

9.3.7 Pharmacokinetic Statistical Methodology

The PK parameters of lasmiditan and its metabolites will be listed and summarized using standard descriptive statistics, including estimates of intra-subject variability as appropriate. Arithmetic mean ($\pm 1 \text{ SD}$) plasma concentration profiles, as well as individual subject profiles, will be presented graphically by treatment over time.

9.4 Pharmacodynamic Assessment

9.4.1 Pharmacodynamic Analysis

The primary endpoint (SDLP) and some of the secondary endpoints (Performance [CogScreen Symbol Digit Coding [SDC] test] and Driving performance endpoints) will be analyzed by CRC, whereas the self-reported secondary endpoints (Karolinska Sleepiness Scale [KSS], Self-Perceived Safety to Drive Question and Visual Analog Scale [VAS] to assess subject's motivation and self-appraisal), will be analyzed by Covance EC Biometrics.

SDLP using the Cognitive Research Corporation Driving Simulator- MiniSim (CRCDS-MiniSim) (reported and analyzed by CRC)

SDLP will be used to assess objective level of driving impairment.

The data will be listed, summarized, and analyzed by treatment as outlined in Section 9.4.2 below.

Self-reported secondary endpoints (reported and analyzed by Covance EC Biometrics)

Karolinska Sleepiness Scale (KSS)

The KSS will be used to assess subjective level of sleepiness. This is a subject self-reported measure of situational sleepiness and provides an assessment of alertness/sleepiness at a particular point in time.

The data will be listed, summarized by treatment in frequency tables, and analyzed as outlined in Section 9.4.2 below.

Self-Perceived Safety to Drive Question

Prior to driving, the subject will be asked a simple question as to whether they feel safe to drive (“Right now do you feel safe to drive?”). Subject will answer “yes” or “no”.

The data will be listed, summarized by treatment in frequency tables, and analyzed as outlined in Section 9.4.2 below.

VAS to Assess Subject’s Motivation and Self-Appraisal

After completing the driving simulation, subjects will assess their own performance and their level of motivation to perform at their best during the driving simulation. Subjects will respond to 2 questions:

1. How well you think you drove for the last 60 minutes?
2. How motivated did you feel to drive at your best during the last 60 minutes of driving?

Subjects will record their response to each question by writing a vertical line on a 100-mm horizontal, linear visual analog scale, indicating their level of performance (0 = Not Satisfactory to 100 = Satisfactory) and motivation (0 = Not Motivated to 100 = Motivated). Scores on the 100-mm linear scale will be measured to the nearest millimeter from the left.

These data will be listed, summarized by treatment, and analyzed as outlined in Section 9.4.2 below.

Performance secondary endpoints (reported and analyzed by CRC)

CogScreen SDC Test

Number of correct responses, accuracy, and standard deviation of reaction time from the CogScreen SDC test will be used to assess treatment-related changes in cognitive functioning.

The data will be listed, summarized, and analyzed by treatment as outlined in Section 9.4.2 below.

Driving performance secondary endpoints (reported and analyzed by CRC)

Lane Exceedance (including number, maximum and duration), Average Speed, Speed Deviation, Speed Count, Excessive Ay (cornering speed threshold exceeded), Total Collisions, and Divided Attention measures (correct responses, omission errors, commission errors, reaction time, standard deviation of reaction time) will be used to assess objective level of driving impairment.

The data will be listed, summarized, and analyzed by treatment as outlined in Section 9.4.2 below.

9.4.2 Pharmacodynamic Statistical Methodology

The primary endpoint, SDLP, will be analyzed using a mixed repeated measures model with fixed effects for sequence, period, and treatment, with repeated observations for subjects for each of the driving time points. An unstructured covariance structure and Kenward-Roger degrees of freedom will be used. In the event an unstructured covariance structure fails to converge, a variance components covariance structure will be assumed. Separate models will be used for each of the driving time points. In addition to assessments of treatment effect, p-values for significance testing of period and sequence effects will be provided.

All secondary endpoints (excluding total collisions and self-reported readiness) will be analyzed for each of the time points using a mixed repeated measures model similar to the one used for the primary analysis, with sequence, period, and treatment as fixed effects, with repeated observations for subject. Separate models will be used for each of the driving and cognition time points. Lane Exceedance will be log transformed as $\ln[x+1]$ prior to analyses.

For the primary and secondary endpoints (excluding total collisions and self-reported readiness), pairwise comparisons of differences in means and the corresponding 95% confidence intervals (CIs) of the differences will be provided at each time point for:

- Lasmiditan 100 mg versus placebo
- Lasmiditan 200 mg versus placebo
- Diphenhydramine 50 mg versus placebo

Example SAS code (mixed model for primary and secondary endpoints, including with data sorted for each endpoint as follows):

```
proc sort data=adxx; by atptn usubjid aperiod; run;

proc mixed data=adxx alpha=0.05;
  by atptn;
  class trtpn aperiod trtseqp usubjid ;
  model aval = aperiod trtpn trtseqp / ddfm=kr;
  repeated / sub=usubjid type=un;
  lsmeans trtpn / cl pdiff alpha=0.05;
  estimate '100 vs. Pbo' trtpn -1 1 0 0 / cl alpha=0.05;
  estimate '200 vs. Pbo' trtpn -1 0 1 0 / cl alpha=0.05;
  estimate 'Dip vs. Pbo' trtpn -1 0 0 1 / cl alpha=0.05;
run;
```

In addition, pair-wise within-subject differences in SDLP greater than 4.4 cm in absolute value (equal to the previously found difference between placebo and 0.05% BAC for the CRCDS) will be compared using McNemar's test. Pair-wise, within subject differences in SDLP will also be tested for symmetry about zero (Laska 2012) using the maximally selected McNemar test).

Summary statistics for raw and change from baseline values will be provided (mean, SD, median, minimum, maximum) for primary and secondary endpoints (excluding total collisions and self-reported readiness) for each time point and treatment group.

Figures will be provided for the within subject difference scores by treatment and time point as both a histogram and scatter plot for SDLP.

Self-reported Readiness to Drive

Pairwise comparisons for readiness to drive will be analyzed using McNemar test.

Example SAS code (Pairwise comparisons for readiness to drive using McNemar test):

```
proc freq data=xxx;
  title "McNemar's test for Paired Samples";
  tables treat1*treat2 /agree expected norow nocol nopercnt;
run;
```

Total Collisions

Summary statistics will be provided (mean, SD, median, minimum, maximum) for total number of collisions for each time point and treatment group. Additionally, differences in number of collisions for each pair-wise comparison will be provided with their corresponding Wilcoxon Signed Rank p-value. A bar chart will be provided pooling total number of collisions by 0, 1, 2, or >=3 for all 4 treatment groups.

Additional analysis may be conducted if deemed appropriate.

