10.3.3. Pharmacodynamic Analyses

The primary endpoint, SDLP, will be analyzed using a mixed model with fixed effects for sequence, period, and treatment, and a random effect for subject within sequence for each of the driving time points. Separate models will be used for each of the driving time points.

Secondary endpoints will be evaluated similarly; however, Lane Exceedance will be log transformed (more specifically, $\ln[x+1]$) prior to analyses. Pairwise comparisons for readiness to drive will be analyzed using McNemar test.

For the primary and secondary endpoints, pairwise comparisons (hypothesis tests) of differences in means, and 95% confidence intervals on differences will be provided at each time point for

1. Lasmiditan 100 mg versus placebo
2. Lasmiditan 200 mg versus placebo
3. Diphenhydramine 50 mg versus placebo

In addition, pairwise within-subject differences in SDLP greater than 4.4 cm in absolute value (equal to the previously found difference between placebo and 0.05% BAC for the CRCDS) will be compared using McNemar test. Furthermore, these pairwise, within-subject differences in SDLP will be tested for symmetry about zero using the maximally selected McNemar test.

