11. CHANGES FROM THE PROTOCOL SPECIFIED STATISTICAL ANALYSES

The mixed model specification was updated to use a REPEATED statement rather than a RANDOM statement in the SAS[®] MIXED procedure, to more readily allow for the estimation of an unstructured covariance matrix. Additional details regarding model specification and outputs are also provided in Section 9.4.2.

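### If the unstructured covariance fails to converge, the SAP's variance-components fallback treats a subject's four periods as independent and loses the crossover's precision

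*SAP*

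**What the plan says.** Protocol section 10.3.3 specifies a mixed model with fixed sequence, period and treatment effects and "a random effect for subject within sequence for each of the driving time points". That random effect carries the correlation between a subject's four periods.

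SAP section 11 records the change: "The mixed model specification was updated to use a REPEATED statement rather than a RANDOM statement". The reason given is that an unstructured matrix is then easier to estimate. The example code in SAP section 9.4.2 has only "repeated / sub=usubjid type=un" and no RANDOM statement.

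The same section then gives the fallback: "In the event an unstructured covariance structure fails to converge, a variance components covariance structure will be assumed". It names no intermediate structure and does not say that a subject effect would be restored. Separate models are fitted at each driving time point. A similar model serves every secondary endpoint except total collisions and readiness to drive. SAP section 3 says that the SAP supersedes the protocol's statistical considerations.

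**The concern.** The label variance components means different things in the two statements. Attached to a random subject effect, it gives a between-subject and a residual variance, and so a common positive correlation within subject. In a REPEATED statement with no RANDOM statement, it gives sigma² times the identity matrix, with zero covariance between a subject's drives. The move from RANDOM to REPEATED therefore changed what the fallback does, and section 11 does not mention this.

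What is at stake if the fallback is used:

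- **Primary noninferiority tests.** Confidence intervals are too wide and true noninferiority can be missed. Testing under SAP section 9.4.3 starts with 100 mg at 24 hours, and alpha passes on only if that test succeeds, so a miss there blocks every later claim.
- **Comparison across time points.** The unstructured fit could converge at one time point and fail at another. Interval widths at 8, 12 and 24 hours would then differ because of the covariance structure, in a study of duration of effect.
- **Secondary endpoints and diphenhydramine versus placebo.** These are difference tests, so an inflated standard error hides impairment or weakens the sensitivity check.
- **Sequence-effect p-values.** The SAP promises these. Under independence they err the other way and are too small.

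**Working it through.** **Inputs (SAP section 7).** "standard deviation (SD) of differences between lasmiditan and placebo within subject for standard deviation of lateral position (SDLP) is approximately 9.5 cm"; "the true difference between lasmiditan doses and placebo is 0"; "the NI margin is proposed to be 4.4 cm". The stated result is that "a sample of 60 subjects would provide >90% power to establish NI of either dose of lasmiditan compared to placebo". The decision rule (SAP section 9.4.3) is that the upper limit of the two-sided 95% interval lies below the margin.

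**Step 1: reproduce the stated power.** SE = 9.5/sqrt(60) = 1.226 cm. Power = Phi(4.4/1.226 − 1.96) = Phi(1.63) = 94.8%. With a noncentral t on 59 df it is 94.2%. Both agree with the stated figure.

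**Step 2: standard error under the fallback.** Let rho be the correlation between two drives of one subject at the same time point.

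- Within-subject SD = 9.5/sqrt(2) = 6.72 cm.
- Total SD = 6.72/sqrt(1 − rho).
- With a diagonal matrix, the model SE of a treatment difference = total SD × sqrt(2/60) = 1.226/sqrt(1 − rho).

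The true sampling SD of the estimate is still 1.226 cm. With complete balanced data the point estimate is the same under both fits; only the reported SE changes.

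**Step 3: chance of passing.** P = Phi((4.4 − 1.96 × model SE)/1.226). For example, at rho = 0.5 the model SE is 1.734, and P = Phi((4.4 − 3.40)/1.226) = Phi(0.82) = 79%.

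The documents give no rho, so the table shows a range. Half-widths use t on 230 df. The last column simulates the 4×4 Williams design (15 subjects per sequence, 5,000 runs per rho, true difference 0) with an independence fit.

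| rho (assumed) | SE factor | Model SE (cm) | 95% half-width (cm) | P(pass), formula | P(pass), simulated |
|---|---|---|---|---|---|
| 0 | 1.00 | 1.23 | 2.42 | 95% | 95% |
| 0.2 | 1.12 | 1.37 | 2.70 | 92% | not run |
| 0.3 | 1.20 | 1.47 | 2.89 | 89% | 88% |
| 0.5 | 1.41 | 1.73 | 3.42 | 79% | 80% |
| 0.6 | 1.58 | 1.94 | 3.82 | 69% | not run |
| 0.7 | 1.83 | 2.24 | 4.41 | 50% | 52% |
| 0.8 | 2.24 | 2.74 | 5.40 | 21% | 23% |

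A fit that keeps the within-subject correlation gave an SE of 1.22 to 1.23 cm and 94% to 95% power at every rho simulated (0, 0.3, 0.5, 0.7, 0.8).

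If all 72 enrolled subjects completed, the fallback would give 94%, 87%, 63% and 32% at rho = 0.3, 0.5, 0.7 and 0.8.

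**Step 4: error rates.** At a true difference of 4.4 cm, the one-sided error is Phi(−1.96/sqrt(1 − rho)). At rho = 0.5 this is Phi(−2.77) = 0.28%, against 2.5% nominal. The sequence test goes the other way: its simulated type I error is 25%, 36% and 48% at rho = 0.3, 0.5 and 0.7, against 5%.

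**The case against.** **The sentence could mean a return to the protocol's model.** Variance components also describes a random subject effect plus a residual. Section 11 ties the move to REPEATED to estimating the unstructured matrix, so if that matrix is abandoned, one might go back to RANDOM. The SAP does not say this. It replaces one covariance structure with another, and its only code is a REPEATED statement. SAP section 9.4.1 also splits the endpoints between two organisations, which could resolve the wording differently. The sentence needs changing on either reading.

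**The event is contingent.** A 4×4 unstructured matrix has 10 parameters and may well converge for SDLP with about 60 subjects. This stands: the planned primary fit is not affected. Sparse secondary counts, such as excessive Ay and commission errors, seem more exposed to failure. That is a judgement, since the documents give nothing on their distribution or correlation.

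**The error is conservative for noninferiority.** This also stands. With positive rho and complete data, a false noninferiority claim becomes less likely. The cost is lost power and, on the secondary difference tests, missed impairment.

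**The loss depends on rho.** At rho = 0 there is none, and at 0.3 power is 89%, only just below the stated figure.

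**Other paired analyses are unaffected.** The McNemar and symmetry tests on SDLP differences do not use this covariance. They do not, however, decide noninferiority.

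**Compound symmetry makes assumptions too.** It imposes equal variances and correlations, and the SE of a given contrast can be too small if these differ. But independence is the special case of compound symmetry with zero correlation, so this objection weighs more heavily on the planned fallback.

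**Conclusion.** The concern holds. Followed as written, the fallback gives a diagonal covariance and wrong error bars for a crossover. With the SAP's own planning inputs the SE is inflated by 1/sqrt(1 − rho). Noninferiority power falls from about 95% to between 89% and 50% for rho from 0.3 to 0.7, and to 21% at 0.8.

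These figures are per comparison and conditional on the unstructured fit failing. They assume 60 complete subjects, a common correlation between periods and a rho that the documents do not supply. The point is worth correcting, but it does not undermine the primary analysis if the unstructured model converges.

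**What to change.** In SAP section 9.4.2, delete the variance-components fallback and specify an ordered one that keeps within-subject correlation: TYPE=CSH in the REPEATED statement, then TYPE=CS if that also fails, with Kenward-Roger degrees of freedom. Alternatively, name the protocol's random subject-within-sequence effect as the fallback; with positive correlation this matches compound symmetry. Show the fallback code beside the main code, apply it to the secondary endpoints as well, and require the report to state which structure was used for each endpoint and time point.

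The cost is one SAP sentence and one code option. Design, data collection and sample size do not change. The equal-correlation assumption that remains is weaker than the independence it replaces.
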